For the second primary endpoint based on postoperative pain, we will collect all NPS pain scores within the 6-hours postoperation and will express results as AUCpain at the patient level. In a retrospective analysis of 37 patients from a similar population (See Section 3.8), mean pain level within the 6-hours postoperation was 1.3 (SD of 0.5) on the **log-transformed NPS scale**.

Sample size calculation is based on the mean AUCIAP and AUCpain within 6-hours postoperation across patients in each arm. We power this study with 2 primary endpoints to detect 20% decrease in IAP (from 13.9 to 11.1, SD of 4) and 25% decrease in pain scores within the 6-hours postoperation (from 1.3 to 0.975; SD of 0.5) with deep vs moderate NMB, with type I error rate of 0.025 for each endpoint. The change in NPS scores (25% or 1 point on the raw scale) is a validated clinically meaningful change. The decrease in pain scores on which the sample size estimate is based on the natural log transformed scores. This calculation assumes independence of the two primary endpoints. We elected to increase the standard deviation of the AUCIAP in this power calculation as a conservative measure because the population from the reference study is different from the population of interest. A total of 120 patients evaluable for each of the primary endpoints will provide 90% power to detect a significant difference in at least one of the two endpoints. This sample size also allows for an interim analysis halfway through enrollment, using O'brien-Fleming boundaries with Lan de Mets spending functions for futility. We base the interim analysis decision rule on both of the primary outcomes. The trial will continue to full enrollment if the interim analysis results for either/both of the primary outcomes reports p<0.755. The trial may be terminated if p>0.755 for both outcomes. We will conclude that the arms are significantly different if p≤0.025 for either of the outcomes. In order to ensure at least 120 patients evaluable for each of the primary endpoints, we plan to randomize at least 130 patients (See Section 13.0 for potential perioperative scenarios).

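### The interim futility cut-off of p = 0.755 is not what the named O'Brien-Fleming/Lan-DeMets method gives at the stated level and power; its derivation and scale need checking

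*Combined protocol and SAP*

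**What the plan says.** All of this is in the combined protocol and SAP, section 14.0 (Biostatistics). The design has two primary endpoints, AUC of intra-abdominal pressure (IAP) and AUC of pain over six hours, "with type I error rate of 0.025 for each endpoint". The sample size is said to be one that "will provide 90% power to detect a significant difference in at least one of the two endpoints", and the endpoints are assumed independent. One interim analysis takes place halfway through enrollment, using O'Brien-Fleming "boundaries with Lan de Mets spending functions for futility". The rule has two halves: "The trial will continue to full enrollment if the interim analysis results for either/both of the primary outcomes reports p<0.755", and "The trial may be terminated if p>0.755 for both outcomes". Success at the end requires p of 0.025 or less on either endpoint.

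The section does not give the beta that is spent, the sidedness of the interim p-value, whether the bound is binding, or any bound on the z scale.

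**The concern.** A plan that names a spending function, a level, a power and a time of look has nearly fixed its futility bound, so the printed number should be recoverable. It is not. The number also looks like a z-value: for the same level and look, 0.755 is the z-bound that goes with 80% power.

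This is the trial's only interim decision threshold based on the primary endpoints. If the number or its scale is wrong, the look will seldom do its job: most trials in which deep block changes neither endpoint would run to full size. The person running the interim analysis also cannot tell from the text which scale or side applies.

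**Working it through.** **Inputs from section 14.0.** IAP 13.9 to 11.1, SD 4. Log pain 1.3 to 0.975, SD 0.5. 120 evaluable, randomised 1:1, so 60 per arm. Level 0.025 per endpoint. One look at t = 0.5. Endpoints independent.

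**Assumptions where the plan is silent.** Two-sided level (final critical value 2.2414), 90% power per endpoint, non-binding bound, no efficacy stop.

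**1. The plan's power.** The drift is θ = δ / (SD × √(2/60)).
- IAP: 2.8 / (4 × 0.1826) = 3.834, power 94.4%.
- Pain: 0.325 / (0.5 × 0.1826) = 3.560, power 90.6%.
- At least one: 1 − (0.056 × 0.094) = 99.5%.

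The stated 90% is therefore reproduced as the power for pain alone, which is why 90% is taken per endpoint below.

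**2. The bound at 90%.** Beta spent at the look is 2 − 2Φ(z₁₋β/₂ / √t). For β = 0.10 this is 2 − 2Φ(1.645 / 0.7071) = 0.020, and Φ⁻¹(0.020) = −2.054. Solving for the drift that makes the total type II error 0.10 gives θ = 3.558. The bound is θ√t + Φ⁻¹(spent) = 2.516 − 2.054 = **0.462**. As a p-value that is **0.322 one-sided or 0.644 two-sided**. Using the plan's own pain drift (3.560) gives 0.464. Reading 0.025 as one-sided gives z = 0.263, p 0.396 or 0.792. None of these is 0.755.

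**3. The bound at 80%.** For β = 0.20 the spent beta is 0.070, Φ⁻¹ = −1.476 and θ = 3.1556. The bound is 2.2313 − 1.4763 = **0.7550**, which is p 0.225 one-sided or 0.450 two-sided. The printed digits match this z-value.

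**4. Can a p-value near 0.755 arise?** Yes, under choices that the plan does not state.
- The same calculation gives two-sided p = 0.758 at β = 0.065 and 0.754 at β = 0.066.
- A two-sided inner-wedge bound with IAP's implied β of 0.056 gives about 0.750 (non-binding) or 0.754 (binding).
- An inner wedge at β = 0.10 with the alternative form 4 − 4Φ(z₁₋β/₄ / √t) gives about 0.766.

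**5. Chance of stopping when neither endpoint has an effect.** With independent endpoints it is the square of the chance for one endpoint. Expected randomised is 130 − 65 × that probability, taking the look at 65 randomised.

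| Rule, required on both endpoints | Stop probability | Expected randomised |
|---|---|---|
| p > 0.755, as printed | 0.245² = 6.0% | 126 |
| two-sided p > 0.644 (90%) | 0.356² = 12.7% | 122 |
| two-sided p > 0.450 (80%) | 0.550² = 30% | 110 |
| z < 0.462, directional (90%) | Φ(0.462)² = 46% | 100 |
| z < 0.755, directional (80%) | Φ(0.755)² = 60% | 91 |

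If the printed p is one-sided, it means z below −0.69 on both, which is also 6.0%. With correlation 0.3 to 0.5 between endpoints, the printed rule stops 6% to 7% of null trials on a two-sided p and 9% to 12% on a one-sided p.

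**6. Chance of a wrong stop.** The interim means of z at the planned effects are 3.834 × 0.7071 = 2.711 (IAP) and 3.560 × 0.7071 = 2.517 (pain).
- Both effects present: z < 0.462 gives 0.0123 × 0.0199 = 0.02%; z < 0.755 gives 0.0252 × 0.0390 = 0.10%. The printed rule gives under 0.01%.
- Only one effect present: z < 0.462 gives 0.678 × 0.0123 = 0.8% or 0.678 × 0.0199 = 1.4%; z < 0.755 gives 0.775 × 0.0252 = 2.0% or 0.775 × 0.0390 = 3.0%.

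**The case against.** **The explanation is not proven.** A reader might infer from the match at z = 0.7550 that a z-bound was certainly copied in as a p-value. The documents do not support that much. They mention 90% power and never 80%, and they leave beta, sidedness and the form of the bound open. Step 4 shows p-values close to 0.755 under some of those open choices. This objection stands against the explanation. It does not rescue the figure, because those choices depart from the stated 90% or from the usual one-sided futility bound, and the plan records none of them.

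**The contrast of 6% with 46% or 60% mixes two things.** This also stands. Like for like, on an undirected p at the stated 90%, the change is from 6.0% to 12.7%; the rest of the gain comes from giving the rule a direction. The requirement that both endpoints fail is deliberate and also lowers the rate: each endpoint alone exceeds 0.755 in 24.5% of null trials. It would therefore be too strong to say that the look never stops a futile trial, or that the number alone is to blame.

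**The harm is limited.** Stopping is optional and the final level is fixed. A cut-off that rarely stops the trial cannot inflate type I error and costs almost no power. A reader might fear for the validity of the final test, but nothing in the plan supports that.

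**The replacement value depends on a decision.** The first value proposed below treats 90% as power per endpoint, whereas the plan words it as power for at least one. The sponsor must confirm what was used.

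**Conclusion.** The point holds in this form: p = 0.755 does not follow from the method, level and power that section 14.0 states. The standard bound is z = 0.46 (one-sided p 0.32, two-sided p 0.64). This rests on a two-sided 0.025 level, 90% per endpoint, exactly half the information, a non-binding rule and no efficacy stop. A z-value for 80% power entered as a p-value is the likeliest origin, but remains an inference.

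As written, the look stops about 6% of trials with no effect on either endpoint, assuming independence. If the p-value is two-sided, a strong effect in the wrong direction on either endpoint also keeps the trial going, although the primary hypotheses are directional. The cost is forgone early stopping, up to roughly 26 to 35 patients on average in a null trial (126 against 100 or 91) if the rule were both corrected and directional. The conclusions of the completed trial are not at risk. This should be corrected, but it is not a fatal flaw.

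**What to change.** Check how 0.755 was derived, and replace both occurrences in section 14.0 with the bound recomputed for the stated design, directional and on its correct scale:

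- For 90% per endpoint: futility if z < 0.46 in favour of deep block (one-sided p > 0.32) on both endpoints.
- Only if the sponsor confirms that 80% per endpoint was used: z < 0.755 (one-sided p > 0.225) on both endpoints.

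State the alpha, beta, sidedness and information fraction behind the bound, and that it is non-binding. The bound should be recomputed if the look is not at exactly half the information: at 90% it moves from 0.462 at t = 0.50 to 0.514 at t = 0.51. Leave the final 0.025 level unchanged.

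The cost is a short rewrite of the interim rule once the sponsor has settled the inputs, with no new data. The downside is a wrong-stop risk of about 0.02% to 0.1% if both planned effects are real, and about 1% to 3% if only one is.

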#### Primary Hypotheses:

- 1) Patients who undergo surgery with a deep NMB technique will report lower postoperative pain.
- 2) Surgeons will operate at lower levels of intra-abdominal pressure under deep NMB technique.

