#### 14.0 BIOSTATISTICS

In this single-blinded prospective randomized study, patients will be randomized in 1:1 ratio to two arms: moderate NMB (control) or deep NMB (intervention). The two primary endpoints of interest in this study are: levels of IAP and postoperative pain. Thus, in the sample size calculation below, we consider multiple primary endpoints and power the trial to detect success in at least one endpoint. The first primary endpoint of interest is IAP. The second primary endpoint of interest is Pain scores within 6-hours post operation. To characterize the entire set of a patient's IAP measurements under insufflation, we consider the use of area under the curve (AUC). We plan to randomize 130 patients to moderate or deep NMB arms, stratified by BMI (< vs >=30) and surgeon, and expect 120 patients to be evaluable for each of the two primary endpoints. Patients are considered evaluable for the first primary endpoint (IAP) if they can provide at least one IAP recording; patients are considered evaluable for the second primary endpoint (Pain) if they can provide at least one NPS pain score within the 6-hours postoperation.

AUC is a useful clinical endpoint for the aggregate effect over time and can summarize the average response to treatment over the period of observation. AUC is an appropriate summary measure for data collected over time, and it is commonly seen in pain measurements, as well as chronic obstructive pulmonary disease (COPD), diabetes, and pharmacokinetics studies. For this study, we will use the area under the IAP curve during insufflation as a measure for the first primary endpoint which focuses on the effect of deep NMB on IAP during robotic prostactetcomy. We will consider the time-weighted measure of AUC that integrates serial

2.1

assessments of the patient's IAP measurement over time using the trapezoidal rule. The corresponding "mean AUC" (AUCmean) is obtained as AUC/duration of insufflation for each patient. From **Kim et al**, mean IAP decreased by approximately 22% (standard deviation [SD] = 1.3) from moderate NMB to deep NMB.

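### The fixed 0.025 threshold for each primary endpoint is valid, but Holm's step-down on the same two p-values would give more power for the two separate primary hypotheses with the same sample size

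*Combined protocol and SAP*

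**What the plan says.** Section 14.0 names two primary endpoints: "The two primary endpoints of interest in this study are: levels of IAP and postoperative pain". The sample size is set "with type I error rate of 0.025 for each endpoint", and the final decision rule is "We will conclude that the arms are significantly different if p≤0.025 for either of the outcomes". No step-down, fallback or other rule for passing alpha between the endpoints appears in the document. A 5% familywise rate is never written out; it is implied by 2 × 0.025.

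The power target is that 120 evaluable patients "will provide 90% power to detect a significant difference in at least one of the two endpoints". The interim analysis is for futility only. It has no efficacy boundary, so it spends no efficacy alpha.

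Section 2.0 lists two primary objectives and two primary hypotheses, one for each endpoint. The pain hypothesis reads "Patients who undergo surgery with a deep NMB technique will report lower postoperative pain"; the other concerns lower operating pressure. Section 14.0 gives each endpoint its own model.

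**The concern.** Two hypotheses are stated separately, so readers of the results will ask separately whether pain fell and whether IAP fell. Under the fixed threshold, a trial with p = 0.001 for IAP and p = 0.03 for pain cannot claim the pain hypothesis. Yet once the IAP null has been rejected at 0.025, only one hypothesis remains, and testing it at 0.05 still holds the familywise error at 5%. What is at stake is a claim on the second endpoint when its p-value falls between 0.025 and 0.05 and the first endpoint has already succeeded.

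**Working it through.** **Inputs, all from Section 14.0 unless marked.** 120 evaluable patients randomised 1:1, so n = 60 per arm. IAP: 13.9 to 11.1, difference 2.8, SD 4. Pain (log scale): 1.3 to 0.975, difference 0.325, SD 0.5. Alpha 0.025 per endpoint; endpoints independent. Assumption: two-sided tests, because the plan does not state sidedness. The futility look is left out; it applies in the same way under either rule.

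**Power per endpoint.** With δ the difference, z = δ / (SD × √(2/n)) and power ≈ Φ(z − c), where c = 2.241 at two-sided 0.025 and 1.960 at two-sided 0.05.

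- IAP: z = 2.8 / (4 × √(2/60)) = 3.834. Power 0.9444 at 0.025 and 0.9695 at 0.05.
- Pain: z = 0.325 / (0.5 × √(2/60)) = 3.560. Power 0.9064 at 0.025 and 0.9452 at 0.05.

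**The plan's own figure.** Power for at least one endpoint = 1 − (1 − 0.9444)(1 − 0.9064) = 0.995. The stated 90% does not reproduce under that label, which would need only about 33 per arm. It does match power for pain alone: 90% at 0.025 needs 59 per arm, 118 in total, against the 120 stated. The comparison below does not depend on this mismatch.

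**Current rule.** Both endpoints: 0.9444 × 0.9064 = 0.856.

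**Holm, under independence.**

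- Pain is declared if its p ≤ 0.025, or if its p lies between 0.025 and 0.05 and IAP has p ≤ 0.025: 0.9064 + (0.9452 − 0.9064) × 0.9444 = 0.943.
- IAP likewise: 0.9444 + (0.9695 − 0.9444) × 0.9064 = 0.967.
- Both are declared if both p ≤ 0.05 and at least one is ≤ 0.025: 0.9695 × 0.9452 − (0.9695 − 0.9444)(0.9452 − 0.9064) = 0.915.
- At least one: unchanged at 0.995, because the first step is the current rule.

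| Power | Fixed 0.025 | Holm |
|---|---|---|
| Pain | 90.6% | 94.3% |
| IAP | 94.4% | 96.7% |
| Both | 85.6% | 91.5% |
| At least one | 99.5% | 99.5% |

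Reaching 91.5% for both under the fixed rule would take about 70 evaluable per arm, or 140 in total (0.9713 × 0.9456 = 0.918 at 70; 0.9693 × 0.9425 = 0.914 at 69).

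**Correlation (assumed values, simulation with 1,000,000 draws per scenario).** At 0.5, power for both goes from 87.1% to 92.1%; at 0.8, from 88.8% to 92.9%. At 0.8 the IAP gain falls to 1.2 points (94.4% to 95.6%).

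**Other effect sizes (assumed, independence).** The pain gain is (0.9452 − 0.9064) multiplied by IAP power at 0.025. For true IAP differences of 2.0, 1.5, 1.0 and 0 it is 2.7, 1.7, 0.7 and 0.1 points. In the other direction, if pain falls by 25% on the raw scale, the log difference is −ln(0.75) = 0.288. Pain power then goes from 81.9% to 88.0%, and power for both from 77.3% to 85.5%.

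**Error rates.** With both nulls true and independent, familywise error is 1 − 0.975² = 4.94% under either rule. With one true null and the planned effect on the other, the error on the null endpoint under Holm is 0.025 + 0.025 × 0.9444 = 4.86% (pain null) or 0.025 + 0.025 × 0.9064 = 4.77% (IAP null), against 2.5% now. The ceiling is 5%. In simulation at correlations of 0, 0.3, 0.5 and 0.8, familywise error did not exceed 5% beyond simulation error.

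**The case against.** A reader might infer that the plan mishandles multiplicity. The documents do not support that: 0.025 + 0.025 = 0.05, the split is pre-specified, and it controls familywise error under any dependence.

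A reader might also infer that Holm raises the power the trial was designed for. It does not. The declared criterion is success on at least one endpoint, and on that the two rules are identical. The largest gain is for winning on both, which the plan does not target. This objection stands in part, but Section 2.0 does state the two hypotheses separately, so power for each is a legitimate interest.

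Third, the gain is modest and conditional. Each endpoint already exceeds 90% on the plan's inputs, and the gain shrinks as the other effect weakens. Section 3.4 itself calls the evidence limited and mixed, so a weak effect is not remote. This stands and limits the size of the point.

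Finally, a reader might infer that the change is free. It needs no patients and leaves familywise error within 5%. It does give up the 2.5% error rate on each endpoint taken alone. Under the fixed split, 97.5% intervals match the tests directly; simultaneous intervals compatible with Holm are less simple. Timing matters too: the plan has an interim look at both primary p-values, and the documents do not show whether it has taken place.

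**Conclusion.** The point holds as an efficiency gain. Holm rejects whatever the fixed rule rejects and sometimes more, at the same N and with familywise error at or below 5% under any correlation. On the plan's inputs the gain is 5.9 points for both endpoints, 3.7 for pain and 2.3 for IAP. These sizes rest on two-sided tests, the stated effects and SDs, and independence; at an assumed correlation of 0.8 the gain for both is 4.1 points. If the other endpoint has no true effect, almost nothing is gained. The current rule is not wrong, and keeping it would leave the trial valid.

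**What to change.** In Section 14.0, replace the final decision sentence with a Holm rule: order the two primary p-values; if the smaller is at most 0.025, declare that endpoint and test the other at 0.05; otherwise declare neither. State that the familywise rate is 5% and whether the tests are two-sided, and say how confidence intervals for the two endpoints will be reported alongside the step-down tests.

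The cost is a short amendment, with no change to sample size, data collection or models. It must be made before any unblinded primary results are seen. If the interim comparison has already been run, the amendment should record that those making the change had not seen it; if they had, the change needs explicit justification or the fixed rule should stay.

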#### 13.0 CRITERIA FOR REMOVAL FROM STUDY

Criteria for removal of subject from the study will include patient death, surgical conversion from robotic to open procedure, intraoperative deterioration in clinical condition that would end a planned procedure.

Patients are considered evaluable for the first primary endpoint (IAP) if they can provide at least one IAP recording; patients are considered evaluable for the second primary endpoint (Pain) if they can provide at least one NPS pain score within 6-hours after surgery. Study data will be analyzed according to a modified intention-to-treat principle ("modified" because patients considered inevaluable for a given primary endpoint will be excluded from the analysis of that endpoint).

The following are a list of possible perioperative scenarios. We expect these to occur extremely infrequently. We anticipate fewer than 10 occurrences during the study period and have planned the protocol accordingly.

- 1) Cancelled surgery
  - Patient will not provide either primary endpoint therefore patients in this category will be excluded from primary analysis
- 2) Patient death
  - For patients who die in the perioperative period, any data up until patient death will be analyzed. These patients may possibly contribute data for only one of the two primary endpoints (IAP)
- Surgical conversion from robotic to open procedure
   Any data up until conversion will be analyzed.

   These patients may possibly contribute data for only one of the two primary endpoints (IAP)
- 4) Intraoperative deterioration in clinical condition that would end planned procedure For patients who experience deterioration in clinical condition that ends planned procedure, any data up until deterioration will be analyzed.
  - However, there will be an investigation to assess the possible (but extraordinarily unlikely) influence of protocol in leading to deterioration.
- 5) Deviation from protocol by giving additional dose of NMB to satisfy surgeon request for better visualization
  - All data in this scenario will be analyzed.. Secondary analysis will be conducted as treated.
- 6) Equipment failure of the neuromuscular train of four monitoring device
  Any data up until failure of neuromuscular train of four monitoring device will be analyzed.patient will
  be considered evaluable for only one of the two primary endpoints (IAP).
- Accidental unblinding of surgeon
   All data will be analyzed.. This will be an evaluable patient.

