Analysis of the primary endpoint which involves IAP will be AUCIAP compared between the two arms using the linear mixed-effects model: randomized arm as the fixed-effect, BMI as the adjustment covariate, with surgeon-level random effects. Transformation of the outcome may be applied if the normality-of-errors assumption is violated. As a secondary analysis, the longitudinal IAP measurements will be analyzed using linear mixed-effects models including time and randomized arm as fixed-effects with stratification variable (BMI), and patient-level random effects, nested within surgeons. In the rare case that the patient's IAP is beyond 15 the surgeon will be unblinded to the IAP, and only the IAP up to the point of unblinding will be included in the analysis. 15 is the conventional goal for the upper limit of IAP at MSKCC. Investigators request they know the IAP at a level of 15, so they can weigh risk/benefit of continuing to operate at that higher threshold of IAP. In this rare occurrence, patients will still be included in the analyses as modified intent-to-treat, including IAP values until IAP-unblinding.

Analysis of the second primary endpoint will be AUCpain within 6-hours postoperation. AUCPain analysis will be conducted with linear mixed-effect model with appropriate transformation for the outcome for normality. The model will include randomized arm as fixed-effects along with stratification variable (BMI), and patient-level random effects, nested within surgeons.

For the primary analyses, all recorded IAP will be analyzed in a modified intent-to-treat fashion. Where a patient randomized to moderate NMB crosses over to deep NMB, all recorded IAP will be analyzed under the randomized arm. As a secondary analysis of the primary outcome, we will perform an as-treated analysis where the set of IAP values will be assigned to the actual intervention received. Correlation between AUCIAP and AUCPain will be summarized using Spearman correlation coefficient. Additionally, the primary endpoints will be summarized between patients with and without neuromonitoring issues (see

Section 13.0). As a sensitivity analysis, planned analyses of both primary endpoints will be repeated after excluding patients with neuromonitoring issues (see Section 13.0).

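### Section 14.0 does not settle whether the primary IAP AUC is cut once the surgeon is told the pressure at 15, and its only divisor is wrong for a cut curve

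*Combined protocol and SAP*

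**What the plan says.** All of the following is in Section 14.0 (Biostatistics) unless stated.

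- **Aim and divisor.** The AUC is chosen "To characterize the entire set of a patient's IAP measurements under insufflation". The mean AUC "is obtained as AUC/duration of insufflation for each patient". No variant is given for a curve that stops early.
- **Cut rule, first statement.** If IAP goes beyond 15 the surgeon is told the value, and "only the IAP up to the point of unblinding will be included in the analysis". This comes directly after the description of the secondary longitudinal model.
- **Cut rule, second statement.** A few lines later, "patients will still be included in the analyses as modified intent-to-treat, including IAP values until IAP-unblinding".
- **All-data rule.** Two paragraphs on: "For the primary analyses, all recorded IAP will be analyzed in a modified intent-to-treat fashion". The next sentence deals with patients who cross from moderate to deep block.
- **Meaning of modified.** Section 13.0 explains the word "because patients considered inevaluable for a given primary endpoint will be excluded from the analysis of that endpoint". It does not mention shortened curves.
- **Trigger.** Section 9.0 alerts the surgeon when IAP *reaches* 15. Section 14.0 says *beyond* 15, but also says that investigators want to know the IAP at a level of 15, "so they can weigh risk/benefit of continuing to operate at that higher threshold of IAP".

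**The concern.** The same patient can receive different scores on a primary endpoint, depending on which sentence of Section 14.0 is followed. Section 14.0 lets either endpoint alone support a conclusion at p≤0.025, so the IAP score should be fixed in advance. If it is left open, the rule and the divisor could be chosen after the data are seen.

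The cut is not neutral. It is set off by high values of the outcome, and it removes what follows. If deep block lowers the pressure surgeons need, as the trial supposes, more control patients than deep-block patients will be cut. The control mean is then pulled down and the difference shrinks. The divisor adds a second problem: a cut area divided by the whole insufflation time gives the lowest scores to the patients with the highest pressures.

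**Working it through.** **1. The plan's own power figure.** The plan states 90% power for at least one endpoint. With 60 per arm and 0.025 per endpoint (two-sided assumed), the noncentrality is difference/(SD × √(2/60)).
- IAP: 2.8/(4 × 0.1826) = 3.83, power 94.0% on 118 df.
- Pain: 0.325/(0.5 × 0.1826) = 3.56, power 90.0%.

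Pain alone therefore supplies about 90%, so a smaller IAP difference cannot bring power for at least one endpoint much below the stated figure. (Under the plan's independence assumption the two together give 1 − 0.060 × 0.100 = 99.4%; that mismatch with 90% is a separate matter.)

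**2. Which rule governs.**
- *For the cut:* it is stated twice, the second time under the modified intent-to-treat label.
- *For all data:* that sentence is the one naming the primary analyses, it carries no exception, and the AUC is introduced as covering the whole set of measurements. Section 13.0 lists several events after which data are kept only up to the event; passing 15 is not among them.

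Neither reading is excluded.

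**3. One patient.** Assumed: start at 9 mmHg (the plan gives only a range of 8 to 10), linear climb to 16 over 60 min, then held. Insufflation is 330 min, the 5.5 h pilot surgery time in Section 4.1, so an upper bound.
- All data: (12.5 × 60 + 16 × 270)/330 = 5070/330 = 15.4.
- Cut on reaching 15, at 60 × 6/7 = 51.4 min: area 12 × 51.4 = 617. Over time to the cut, 12.0; over full time, 617/330 = 1.9.
- Cut on reaching 16, at 60 min: area 750. Over time to the cut, 12.5; over full time, 750/330 = 2.3.

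This patient was never below 9 mmHg. As one of 60 controls, and with the cut at 15, the patient moves the control mean by (15.36 − 12.0)/60 = 0.06 or (15.36 − 1.87)/60 = 0.22 mmHg, depending on the divisor.

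**4. Trial level, low crossing rates.** The documents give no crossing rate. Simulation used 200,000 patients per arm, the same curve shape, readings every 15 min, and a cut at the first reading above 15 (that reading counted or not). Patient means are normal with SD 1.3 (the cited study's SD in Section 14.0), control means 11.5, 12.0 or 12.5 (assumed), and a 20% reduction. Pressure is held after the alert. A patient crosses when the time-weighted mean exceeds (12 × 60 + 15 × 270)/330 = 14.45.

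| Controls crossing | All data | Cut, time to cut | Cut, full time |
|---|---|---|---|
| 1.1% | 2.30 | 2.26–2.27 | 2.15–2.16 |
| 3.0% | 2.40 | 2.30–2.32 | 2.01–2.03 |
| 6.6% | 2.50 | 2.27–2.32 | 1.61–1.66 |

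With time to the cut as divisor, the shift runs from 2.30 − 2.27 = 0.03 to 2.50 − 2.27 = 0.23 mmHg.

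If pressure is instead lowered after the alert, the all-data difference in the 6.6% run becomes 2.31 (lowered to 12, for illustration) or 2.21 (to 10). Against 2.27–2.32 for the cut version, the shift vanishes or reverses.

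**5. No true effect.** If arm affects neither pressure nor what follows the alert, the curves are exchangeable between arms. Any one of these scorings, fixed in advance, then has expected difference zero.

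**6. Trigger.** Section 4.2 allows changes in 1 mmHg steps, so *reaches* and *beyond* 15 are one step apart. A patient who climbs from 9 to exactly 15 over 60 min and stays there scores 14.45 uncut or 12.0 cut.

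**The case against.** The strongest reply is that there is no conflict. The cut is specific and stated twice, and the second statement refers to analyses in the plural. The all-data sentence leads into crossover, so its purpose may be only to fix the arm under which data are analysed. Reading the cut as an exception is natural and may be what was meant. But no sentence says so, and for a primary endpoint it should be said.

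Nor does the text show that all recorded IAP is the plan's real rule; that would contradict two of its sentences. A reader might draw support from Section 13.0, where "Accidental unblinding of surgeon" leaves all data in. That concerns a protocol violation, not a planned disclosure at a threshold, and does not decide the matter.

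On the divisor, a careful analyst would probably divide by observed time, since Section 14.0 describes the AUC as time-weighted over the period of observation. A score near 2 mmHg would look wrong at once. That lowers the practical risk, but the only written divisor still gives that score.

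A reader might also infer from the planning values that crossing will be common: a normal model with mean 13.9 and SD 4 puts 39% of control patient means above 15. The documents do not support this as a forecast. The plan calls the event rare and says the SD was deliberately increased, and the same model for the deep arm (mean 11.1) puts 22% of patients below 8 mmHg, under the starting range.

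**Conclusion.** The concern holds as a gap in the specification of a primary endpoint. Section 14.0 leaves open whether the primary AUC is cut when the surgeon is told the pressure, gives no suitable divisor if it is, and describes the trigger in more than one way.

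The expected numerical effect is small: about 0.03 to 0.23 mmHg, usually towards a smaller difference, and nil or reversed if pressure is lowered after the alert. This rests on the assumed curves, on 1% to 7% of controls crossing, and on time to the cut as divisor. The literal divisor would do more damage.

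It would go too far to infer that the IAP comparison is biased when there is no effect, or that the trial is underpowered. Each rule fixed in advance is fair under the null, and power for at least one endpoint is secured by pain if its planned effect is real. The point should be fixed because it concerns a primary endpoint and the remedy is cheap.

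**What to change.** Before analysis, state in Section 14.0 which rule governs the primary AUC for IAP.

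- **All recorded IAP to the end of insufflation** avoids truncation triggered by the outcome. It requires amending both cut sentences.
- **IAP in the blinded period** is also defensible, because the design relies on surgeons not knowing the pressure. It requires a stated reason and an explicit exception in the all-data sentence.

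Under either choice:
- divide any cut curve by the time from start of insufflation to the cut, not by full insufflation time;
- run the other version as a sensitivity analysis;
- report the number unblinded at 15 by arm;
- reconcile the trigger wording in Sections 9.0 and 14.0.

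The cost is a few sentences and one extra analysis on readings already taken every 15 minutes and at each change. The drawback of the all-data version is that values after the alert may reflect the surgeon's knowledge of the pressure; showing both versions makes that visible.
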